10.2.3 Interim Analyses

There will not be any planned interim analyses for efficacy assessments.

10.3 Safety Analyses

Safety parameters for each patient include vital signs, laboratory testing, including chemistry panel and complete blood count, and AE reporting, including AEs resulting from active concomitant standard of care medication. These parameters will be tabulated in line listings along with basic demographic information such as sex and age by clinical site and by treatment arms.

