2.2 Secondary Objectives

- To assess the effect of ECP versus corticosteroids on plasma levels of immunological factors and the frequency of circulating myelin-reactive Th1 and Th17 cells
- To determine whether changes in immunological parameters that occur following initiation of ECP or corticosteroids correlate with clinical outcomes
- To assess the impact of ECP versus corticosteroids on Expanded Disability Status Scale (EDSS) scores every 3 months through 2 years compared to baseline
- To assess the impact of ECP versus corticosteroids on MSFC three dimensional composite z-score every 3 months through 2 years compared to baseline
- To assess the effect of ECP on risk of clinical relapse
- To assess the effect of ECP versus corticosteroids on the frequency of gadolinium-enhancing T1 weighted lesions on cranial MRI scans obtained at months 6 and 12 compared to baseline
- To assess the effect of ECP versus corticosteroids on interval changes in T2 weighted lesion number and volume at months 6 and 12 compared to baseline.
- To assess the tolerability and the safety profiles of ECP versus corticosteroids

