3. OVERALL DESIGN AND PLAN OF THE STUDY

3.1 Overview

This is a Phase II randomized, open-label study to evaluate the efficacy of extracorporeal photopheresis (ECP) versus IVMP on disability progression in subjects with SPMS. At the initial screening visit, an extensive medical history will be obtained and a detailed neurological examination will be performed to determine eligibility. Subjects who meet eligibility criteria will be enrolled in one of two study arms. Subjects will be randomized at a 1:1 ratio to receive ECP (study arm) or active treatment with intravenous methylprednisolone pulses (control arm) administered every 4 Weeks (1 gram per infusion) for 52 weeks.

ECP will be administered according to the following schedule:

Study Arm: Weeks 1-8: 3 times per week

Weeks 9-16: Twice per week

Weeks 17-36: Treatment on two consecutive days every 2 weeks (or optionally, one treatment per week)

Weeks 37-43: Once every 2 weeks

Weeks 44-52: Once every 4 Weeks

[figure not shown]
All subjects, including patients who receive corticosteroids, will be evaluated using the MSFC tool at baseline and every 3 months through 2 years (See Section 9.1 for timing of the schedule of assessments). They will also be scored using the EDSS at baseline and every 3 months through 2 years. Subjects in the control arm will be evaluated by MSFC and EDSS during the week prior to their next intravenous methylprednisolone infusion. Blood will be collected for immune function (cytokines) testing at baseline, and months 3, 6, 9 and 12. MRI will be done at baseline as well as months 6 and 12 following initiation of treatment; if the disability measurements are stable or improved at any point in time, then ECP will be continued per protocol..

Patients in the ECP arm should have all of their treatments with the CELLEX[®] System. Patients randomized to the ECP arm must receive their treatment within 5 days of baseline visit.

In the ECP process, UVADEX[®] (methoxsalen) Sterile Solution will be injected directly the recirculation bag of the extracorporeal circuit after completion of the buffy coat collection. The dose of UVADEX[®] (methoxsalen) Sterile Solution will be calculated based on the standard treatment volume formula (See Section 6.2).

For the schedule of assessments, please refer to Section 0.

Figure 1: Study Design

ECP=Extracorporeal Photopheresis MRI: Magnetic Resonance Imaging

¹ Frequency of ECP treatments:

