8.2.3 Laboratory Parameters

Clinical laboratory assessments will be performed by the UM Hospital Clinical Laboratory at the University of Michigan. Research laboratory studies to measure immunological parameters will be conducted the Neuroimmunology Research Laboratory in the Department of Neurology at the University of Michigan ([name], Director).

Blood samples should be taken using standard venipuncture techniques. Blood samples should be processed according to the procedure described in the laboratory manual.

Laboratory parameters will be determined in accordance with the Schedule of Assessments on Table 2.

Table 1: Laboratory Assessments

Hematology:	Complete CBC
Chemistry:	Creatinine Glucose Triglycerides Urea Uric acid Bilirubin Cholesterol Sodium Potassium
Liver Function Tests	Alkaline phosphatase Aspartate transaminase Alanine transaminase
Immune Parameters	Myelin basic protein –specific IFN γ or IL-17 producing PBMC, Frequency of tetanus toxoid –specific IFN γ or IL-17 producing PBMC, plasma levels of IFN γ , IL-17, IL-4, IL-10, IL-12, IL-21, IL- 23, CCL2, GRO α , CXCL8, CXCL10, CCL11, CXCL13, GM-CSF, G-CSF and neutrophil elastase

Clinically significant laboratory abnormalities should be recorded as AEs according to investigator's judgment. The maximum total amount of blood that will be taken during the study from an individual patient for research studies is 60 ml per blood draw. There will be a total of five blood draws, separated by intervals of 9 weeks or longer. Patients on ECP will have an additional blood draw of 5 ccs prior to every procedure to determine hematocrit and platelet count.

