9. STUDY CONDUCT

9.1 Schedule of Assessments

The schedule of assessments is shown in months, as it facilitates better comprehension, preventing potential errors, in the interpretation of the exact timing for each assessment. On the other hand, in order to facilitate integration with the weekly-based schedule of ECP, and also budget considerations, we use the following transformation between weeks and months when addressing the schedule of assessments:

- a- 3 months: Week 12 \pm 2 week
- b- 6 months: Week 24 \pm 2week
- c- 9 months: Week 36 \pm 2 week
- d- 12 months or 1 year: Week 52 \pm 1 month

The schedule of assessments is shown in Table 2.

Table 2: Schedule of Assessments

Procedures	Screening (-30days)	Baseline ⁵ (Week 2)	Month 3	Month 6	Month 9	12 months/1year	Til End of Study (every 3 months through 2 years) ⁸
Informed Consent	X						
Inclusion/Exclusion Criteria	X						
Vital Signs		X	X	X	X	X	
Medical History/ Interim History ¹	X	X	X	X	X	X	
Physical Examination		X	X	X	X	X	
MSFC ⁸		X	X	X	X	X	X
EDSS ⁸		X	X	X	X	X	X
MRI		X		X		X	
Pregnancy Test ²	X						
Immune Parameters Measurement		X	X	X	X	X	
Clinical Laboratory Tests ³	X	X				X	
Pre-study/Concomitant MedicationsMRI	X	XX	X	XX	X	XX	
Adverse Events	X	X	X	X	X	X	
Randomization to ECP ^{5,6} vs IVMP ⁷	X						

¹ Including history of MS, progression from RRMS to onset of SPMS. A complete history at start of study and interim history at each visit.

²For women of childbearing potential.

³ Both at screening and prior to each ECP procedure, a small amount of blood (2-4 teaspoons) will be drawn to evaluate CBC and chemistries.

⁴Subjects will be randomized at a 1:1 ratio to either ECP.or IVMP

⁵Patients should have ECP within 14 days of baseline visit.

⁶The frequency of ECP treatments will be:

Weeks 1-8: 3 x/ week

Weeks 9-16: 2x/week

Weeks 17-36: 2x/2 weeks

Weeks 37-43: 1x / every 2 weeks

Weeks 44-52: 1x/ every 4 Weeks

⁷ Corticosteroid is administered on a pulse basis and consists of 1 gram of methylprednisolone I.V. every 4 Weeks for 52 Weeks.

⁸These test will occur every three month through 2 years.

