10.2.2 Analysis of Secondary Endpoints

The secondary endpoints include:

- Change in Plasma levels of Immunological Factors and Frequencies of IFN γ and IL-17 MBP-specific PBMC at months 3, 6, 9 and 12 compared with baseline
- MSFC 3 dimensional composite z-score at every 3 month time point through 2 years compared to baseline
- Expanded Disability Status Scale (EDSS) score at every 3 month time point through 2 years compared to baseline
- Percentage of subjects with improvement (as defined for the primary endpoint) at months 3, 6, 9 and 12 compared to baseline
- Occurrence of clinical relapse at any point in the study

- Interval change in T2 lesion number and volume on MRI scans obtained at months 6 and 12 compared to baseline
- The number and volume of gadolinium enhancing lesions on MRI scans obtained at months 6 and 12 compared to baseline
- Interval change in the number and volume of gadolinium enhancing lesions on MRI scans obtained at months 6 and 12 compared to baseline.
- Toxicity and Adverse events in both arms

For continuous outcomes, two-sample t-tests or Wilcoxon rank sum tests will be used to compare the treatment arms. For categorical outcomes, Chi-square tests or Fisher's exact test will be used to compare the treatment arms. The proportion of subjects who experience adverse events and serious adverse events will be summarized by treatment group descriptively; no inferential tests will be performed.

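### Section 10.3 plans only by-arm line listings for vital signs, chemistry and CBC; descriptive by-arm summaries at visits shared by both arms would be a cheap, minor improvement

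*Combined protocol and SAP*

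**What the plan says.** Section 2.2 sets as a secondary objective: "To assess the tolerability and the safety profiles of ECP versus corticosteroids". Section 10.3 counts vital signs, the chemistry panel, CBC and AE reports as safety parameters, and then states the output: "These parameters will be tabulated in line listings along with basic demographic information such as sex and age by clinical site and by treatment arms". It mentions no mean, median, change from baseline, shift table or proportion abnormal.

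Section 10.2.2 supplies the one by-arm safety summary: "The proportion of subjects who experience adverse events and serious adverse events will be summarized by treatment group descriptively; no inferential tests will be performed". That section also lists toxicity as a secondary endpoint, but nothing there defines it by laboratory values or vital signs.

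Laboratory findings reach the AE summary through Section 8.2.3: "Clinically significant laboratory abnormalities should be recorded as AEs", with the decision left to the investigator. The same section adds blood sampling in one arm only: "Patients on ECP will have an additional blood draw of 5 ccs prior to every procedure to determine hematocrit and platelet count".

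**The concern.** A line listing shows patient-level rows. Sorting it by arm does not give an estimate for either arm. As the plan stands, laboratory harms are therefore compared between arms only through AE proportions, and two things make those a weak basis. First, an abnormal value becomes an AE only if an investigator who knows the treatment judges it clinically significant. Second, an abnormality without symptoms can be recorded only if blood is drawn, and blood is drawn far more often under ECP.

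The risks in question are named in the protocol. Appendix 3 lists hypertension, potassium loss, reduced carbohydrate tolerance and liver enzyme rises for corticosteroids; Appendix 4 describes hypotension from volume shifts for ECP. Blood pressure, glucose, potassium and liver enzymes are all measured. Yet the values that both arms provide on the same schedule, which are free of the unequal testing, would only be listed.

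**Working it through.** The plan gives no figure on this point, so the check compares testing schedules and then asks what a summary could resolve.

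**1. Visits common to both arms (Table 2, Section 9.1).** Vital signs: baseline and months 3, 6, 9 and 12. Clinical laboratory tests: screening, baseline and month 12. The shared post-baseline visits are therefore four for vital signs and one for laboratory values.

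**2. Extra draws under ECP (Section 6.2 schedule, full adherence assumed).**
- Weeks 1-8, three per week: 8 × 3 = 24
- Weeks 9-16, two per week: 8 × 2 = 16
- Weeks 17-36, two per fortnight or one per week: 20
- Weeks 37-43, one per fortnight: 3 to 4
- Weeks 44-52, one every 4 weeks: 2 to 3

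Total: 24 + 16 + 20 + (3 to 4) + (2 to 3) = 65 to 67. The slightly different week boundaries in the synopsis give 24 + 16 + 20 + 4 + 2 = 66. Each session has a prior draw for CBC or haematocrit and platelets. A control has one scheduled on-treatment draw.

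**3. Chemistry under ECP is unclear.** The sections differ:
- Section 8.2.3 mentions only haematocrit and platelets for the pre-procedure draw.
- Table 2, footnote 3, says "prior to each ECP procedure, a small amount of blood (2-4 teaspoons) will be drawn to evaluate CBC and chemistries". On that reading chemistry is taken at all 65 to 67 sessions.
- Section 9.2.4 (month 3) asks for CBC or other routine tests as needed, at least weekly.
- Section 9.2.5 (month 6) asks for the full Table 1 panel before each session.

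If only the month 6 text brings in chemistry, and from week 24, the count is (12 to 14) + (3 to 4) + (2 to 3) = 17 to 21. From week 17 it is 20 + (3 to 4) + (2 to 3) = 25 to 27. If the weekly minimum in Section 9.2.4 includes chemistry through weeks 1-16, it is 16 + (25 to 27) = 41 to 43. The imbalance in chemistry therefore cannot be put at one figure.

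**4. Precision of a by-arm summary.** Input: 33 per arm (Section 10.4), complete data assumed. The 95% half-width for a difference in mean change, in SD units, is t(0.975, 64) × √(2/33) = 1.998 × 0.246 = 0.49. Only moderate or larger shifts would be resolved.

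**5. Timing of the control laboratory draw.** Section 9.1 sets "12 months or 1 year: Week 52", plus or minus 1 month (30.4/7 = 4.3 weeks). Assumption: the first pulse is in week 1. Pulses then fall in weeks 1, 5, ..., 49, which is 13 pulses. The window runs from about week 47.7 to week 56.3. The draw could fall within days of the week 49 pulse, or as late as 56.3 − 49 = 7.3 weeks after it.

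**The case against.** The strongest reply is that this is a single-centre phase II trial of 66 patients and its comparative safety objective already has a by-arm analysis. Clinically significant laboratory abnormalities are recorded as AEs and so enter that analysis. This stands to a point: a reader might infer that the plan has no by-arm safety analysis, and Section 10.2.2 shows that it has one. What remains is that laboratory values enter it only after unblinded judgement and at unequal testing rates.

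It can also be said that toxicity is a listed secondary endpoint and that Section 10.2.2 gives general methods for continuous and categorical outcomes. But toxicity is not tied to laboratory values or vital signs, and Section 10.3, the section that deals with those, says listings. The monitoring board's quarterly look at laboratory data of interest (Section 8.2.2.6) is monitoring and gives readers no by-arm estimate.

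The objection that the gain is small is fair. The shared laboratory comparison is one time point, when ECP is least frequent.

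Three stronger readings are tempting and not supported:
- A reader might infer that control values are trough values, since "Subjects in the control arm will be evaluated by MSFC and EDSS during the week prior to their next intravenous methylprednisolone infusion". That sentence covers MSFC and EDSS only. Extending it to vital signs is an inference from shared visits, and it can fail for the month 12 draw, as step 5 shows.
- A reader might take ECP chemistry to be tested at every session. Only the Table 2 footnote says so.
- A reader might want AEs found only on a pre-ECP draw flagged. The AE report contents in Section 8.2.2.4 do not include how an event was detected, so that would need new data collection.

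**Conclusion.** The point holds as a cheap improvement of minor severity. Section 10.3 specifies listings only, and a descriptive by-arm summary at shared visits is a better method for values that Table 2 already schedules. It lets the trial describe comparative safety without relying only on AE counts from unequal testing.

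The documents do not support calling the safety analysis invalid, nor do they allow the size of any distortion in AE proportions to be estimated. No planned test, error rate, power figure or sample size changes.

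The counts and precision assume full ECP adherence and complete data; withdrawals (Section 5) would lower the first and widen the 0.49 SD. The laboratory part also assumes that the month 12 draw in Table 2 applies to controls. The text of Section 9.2.7 mentions Table 1 bloods only before ECP, so this should be confirmed, although it is a matter of clarification and not part of the finding.

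**What to change.** Add to Section 10.3:

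> Vital signs, chemistry and CBC values, including white cells, will be summarised descriptively by arm as change from baseline with 95% CI, with shift tables against the reference range for laboratory values, at visits scheduled in both arms only (vital signs months 3, 6, 9 and 12; laboratory month 12). Pre-ECP laboratory values will be summarised within the ECP arm only. Time since the last infusion will be reported beside the control summaries, which cannot exclude transient post-infusion effects. Listings are supportive; no hypothesis tests.

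The cost is a few sentences, a few tables and a little programming. On the Table 2 reading, no visit or sample is added. Time since infusion should be derivable from the treatment and visit records described in Section 7.4. The main downside is that one shared on-treatment laboratory time point could reassure more than it should, which is why the note on post-infusion effects belongs beside the tables.

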10.4 Determination of Sample Size

Assuming that the proportion of subjects in the corticosteroid treatment who show no evidence of clinical progression at 52 (12 months) is 30%, 66 subjects (33 per treatment arm) provides at least 80% power to detect a treatment difference of 30% (i.e., 60% of the ECP treated subjects will show no evidence of clinical progression at 12 months), based on the normal approximation of the binomial distribution and a one-sided Type I error of 5%.

11. ETHICAL, LEGAL, AND ADMINISTRATIVE ASPECTS

11.1 Data Quality Assurance

This is an investigator initiated research protocol. The investigator will assure that the study will be conducted according to Good Clinical Practice Guidelines as outlined in ICH E6. The investigative team will prepare the CRFs needed for the study.

The investigator will prepare and maintain adequate and accurate case histories designed to record all observations and other data pertinent to the study for each study participant. All information recorded on the CRFs for this study must be consistent with the patients' source documentation (i.e., medical records).

11.2 Case Report Forms and Source Documentation

The CRF's will be the basis for data entry for this study. The investigator will assure that the data are correctly entered into the CRFs and the study monitor for the study will assure that this corresponds to the source documentation. Any discrepancies will be corrected as needed and signed off by the investigator.

11.2.1 Data Collection

Access and right to the CRFs will be carefully controlled and configured according to each individual's role throughout the study. In general, only the investigator and authorized staff will be able to enter data and make corrections in the CRFs.

The CRF should be completed for each patient included in the study and should reflect the latest observations on the patients participating in the study. Therefore, the CRFs are to be completed as soon as possible during or immediately after the patient's visit or assessment. The investigator must verify that all data entries in the CRF are accurate and correct. If some assessments cannot be done, or if certain information is unavailable, not applicable or unknown, the Investigator should indicate this in the CRF. Manual checks will identify any clinical data discrepancies for resolution. Corresponding queries will be loaded into the system and the site will be informed about new issues to be resolved on-line. All discrepancies will be solved on-line directly by the Investigator or by authorized staff. Off-line edit checks will be done to examine relationships over time and across panels to facilitate quality data.

After completion, the investigator will be required to sign off the clinical data

Data about all study drugs dispensed to the patient will be tracked on CRFs.

11.3 Access to Source Data

During the course of the study, a designated clinical monitor will review protocol compliance, compare CRFs and individual patient's medical records, assess drug accountability, and ensure that the study is being conducted according to pertinent regulatory requirements. CRF entries will be verified with source documentation. The review of medical records will be performed in a manner to ensure that patient confidentiality is maintained.

Checking of the CRFs for completeness and clarity, and crosschecking with source documents, will be required to monitor the progress of the study. Moreover, regulatory authorities, Institutional Review Boards (IRBs) may wish to carry out such source data checks and/or on-site audit inspections. Direct access to source data will be required for these inspections and audits; they will be carried out giving due consideration to data protection and medical confidentiality.

11.4 Data Processing

All data will be entered by site personnel into the CRFs.

The Data Cleaning Specification, to be developed during the initiation phase of the study, will include specifications for consistency and plausibility checks on data, and also include rules for data handling (e.g. what fields are entered for Screen Failures).

Previous and concomitant medications will be coded using the World Health Organization (WHO) Drug Reference List (DRL), which employs the ATC classification system. Medical history/current medical conditions and AEs will be coded using the Medical dictionary for regulatory activities (MedDRA) terminology.

The versions of the coding dictionaries can be obtained or provided by Therakos.

11.5 Archiving Study Records

According to International Conference on Harmonization (ICH) guidelines, essential documents should be retained for a minimum of 2 years after final publication and until there are no pending or contemplated publication or at least 2 years have elapsed since the formal discontinuation of clinical development of the investigational product. However, these documents should be retained for a longer period if required by the applicable legal requirements.

11.6 Good Clinical Practice

The procedures set out in this study protocol are designed to ensure that the study will be conducted in accordance with the principles of the Good Clinical Practice guidelines of the ICH, and of the Declaration of Helsinki (1996). The study also will be carried out in keeping with local legal requirements.

11.7 Informed Consent

Before each patient is admitted to the study, informed consent will be obtained from the patient (or his/her legally authorized representative) according to the regulatory and legal requirements of the participating country. This consent form must be dated and retained by the investigator as part of the study records. The investigator will not undertake any investigation specifically required only for the clinical study until valid consent has been obtained. The terms of the consent and when it was obtained must also be documented in the CRF.

If a protocol amendment is required, the informed consent form may need to be revised to reflect the changes to the protocol. If the IRB requests, patients that are currently enrolled in the study will be re-consented with the revised consent.

